4.3. Exclusion criteria for enrolment

Deviations from exclusion criteria are not allowed because they can potentially jeopardise the scientific integrity of the study, regulatory acceptability or subject safety. Therefore, adherence to the criteria as specified in the protocol is essential.

The following criteria should be checked at the time of study entry. If ANY exclusion criterion applies, the subject must not be included in the study:

- Use of any investigational or non-registered product (drug or vaccine) other than the study vaccine during the period starting 30 days before the dose of study vaccine, or planned use during the study period.
- Chronic administration (defined as more than 14 days in total) of immunosuppressants or other immune-modifying drugs within six months prior to the vaccine dose. For corticosteroids, this will mean prednisone ≥ 20 mg/day, or equivalent. Inhaled and topical steroids are allowed.
- Administration of long-acting immune-modifying drugs at any time during the study period (e.g. infliximab).
- Previous hepatitis B booster vaccination since completion of the primary vaccination series with three or four doses of *Engerix-B*.
- Planned administration of a vaccine not foreseen by the study protocol within 30 days preceding the dose of study vaccine, or planned administration during the study period, with the exception of seasonal influenza vaccine.
- Any medical condition that in the judgment of the investigator places the subject at undue risk by participating in the study.
- Concurrently participating in another clinical study, at any time during the study period, in which the subject has been or will be exposed to an investigational or a non-investigational vaccine/product (pharmaceutical product or device).
- History of hepatitis B disease or episode of jaundice with unknown etiology.
- History of any reaction or hypersensitivity likely to be exacerbated by any component of the vaccine.
- Any confirmed or suspected immunosuppressive or immunodeficient condition, based on medical history and physical examination (no laboratory testing required).
- Major congenital defects or serious chronic illness (including insulin-dependent diabetes).
- Acute disease and/or fever at the time of enrolment.
 - Fever is defined as temperature $\geq 37.5^{\circ}\text{C}$ for oral, axillary or tympanic route, or $\geq 38.0^{\circ}\text{C}$ on rectal route.
 - Subjects with a minor illness (such as mild diarrhoea, mild upper respiratory infection) without fever may be enrolled at the discretion of the investigator.
- Administration of immunoglobulins and/or any blood products during the period starting 3 months before the dose of study vaccine, or planned administration during the study period.
- Drug and/ or alcohol abuse within the last 5 years.

5. CONDUCT OF THE STUDY

5.1. Regulatory and ethical considerations, including the informed consent process

The study will be conducted in accordance with all applicable regulatory requirements.

The study will be conducted in accordance with the ICH Guideline for Good Clinical Practice (GCP), all applicable subject privacy requirements and the guiding principles of the Declaration of Helsinki.

GSK will obtain favourable opinion/approval to conduct the study from the appropriate regulatory agency, in accordance with applicable regulatory requirements, prior to a site initiating the study in that country.

Conduct of the study includes, but is not limited to, the following:

- Institutional Review Board (IRB)/Independent Ethics Committee (IEC) review and favourable opinion/approval of study protocol and any subsequent amendments.
- Subject informed consent.
- Investigator reporting requirements as stated in the protocol.

GSK will provide full details of the above procedures to the investigator, either verbally, in writing, or both.

Freely given and written or witnessed/ thumb printed informed consent must be obtained from each subject prior to participation in the study.

GSK Biologicals will prepare a model Informed Consent Form (ICF) which will embody the ICH GCP and GSK Biologicals required elements. While it is strongly recommended that this model ICF is to be followed as closely as possible, the informed consent requirements given in this document are not intended to pre-empt any local regulations which require additional information to be disclosed for informed consent to be legally effective. Clinical judgement, local regulations and requirements should guide the final structure and content of the local version of the ICF.

The investigator has the final responsibility for the final presentation of the ICF, respecting the mandatory requirements of local regulations. The ICF generated by the investigator with the assistance of the sponsor's representative must be acceptable to GSK Biologicals and be approved (along with the protocol, and any other necessary documentation) by the IRB/IEC.

5.2. Subject identification and randomisation of treatment

5.2.1. Subject identification

Subject identification numbers will be assigned sequentially to the subjects who have consented to participate in the study, according to the range of subject identification numbers allocated to each study centre.

5.2.2. Randomisation of treatment

5.2.2.1. Randomisation of supplies

The randomisation of supplies will be performed at GSK Biologicals, using MATerial EXcellence (MATEX), a program developed for use in Statistical Analysis System (SAS®) (Cary, NC, USA) by GSK Biologicals. Entire blocks will be shipped to the study centres /warehouse(s).

To allow GSK Biologicals to take advantage of greater rates of recruitment than anticipated at individual centres in this multi-centre study and to thus reduce the overall study recruitment period, an over-randomisation of supplies will be prepared.

5.2.2.2. Treatment allocation to the subject

The treatment numbers will be allocated by dose.

5.2.2.2.1. Study group and treatment number allocation

The enrolment will be performed to ensure equal distribution of approximately 100 subjects across the two age strata (40 to 50 years and 51-60 years). Therefore, the expected distribution of subjects is as shown in [Table 4](#).

Table 4 Number of subjects required for enrolment

Age Stratum	Vaccine	N
40-50 years	Engerix B	50
51-60 years	Engerix B	50

N = number of subjects to be enrolled

Allocation of a treatment number to the subject at the investigator site will be performed using a randomisation system on internet (SBIR).

After obtaining the signed and dated ICF from the subject and having checked the eligibility of the subject, the study staff in charge of the vaccine administration will access SBIR. Upon providing the age (40 to 50 years and 51 to 60 years) and the subject identification number, the randomisation system will determine the age group and will provide the treatment number to be used for the dose.

The number of each administered treatment must be recorded in the eCRF on the Vaccine Administration screen.

When SBIR is not available, please refer to the SBIR user guide or the Study Procedures Manual (SPM) for specific instructions.

Note that as soon as the target number of approximately 50 subjects in a specific age group has been reached, the enrolment will be frozen for this age group.

5.3. Method of blinding

This is an open-label study as all the subjects will receive a single challenge dose of *Engerix-B*.

The laboratory in charge of the laboratory testing will be blinded to the treatment, and codes will be used to link the subject and study (without any link to the treatment attributed to the subject) to each sample.

5.4. General study aspects

Supplementary study conduct information not mandated to be present in this protocol is provided in the accompanying SPM. The SPM provides the investigator and the site personnel with administrative and detailed technical information that does not impact the safety of the subjects.

5.5. Outline of study procedures

The list of study procedures are provided in [Table 5](#).

Table 5 List of study procedures

Epoch	Epoch 001		
	Visit 1	Visit 2	Visit 3
Type of contact	Day 0	Day 7	Day 30
Sampling time-points	PRE	PD7	PD30
Informed consent	●		
Check inclusion/exclusion criteria	●		
Collect demographic data	●		
Medical history	●		
Hepatitis B vaccination history [†]	●		
Physical examination*	●	0	0
Measure/record height and weight	●		
Check contraindications to vaccination	0		
Pre-vaccination urine pregnancy test for female subjects of child bearing potential	●		
Pre-vaccination body temperature measurement	●		
Treatment number allocation	0		
Blood sampling for antibody determination (~5 ml)	●	●	●
Blood sampling for CMI response (~27 ml)	●	●	●
Vaccine administration	●		
Observation of the subjects for at least 30 minutes after vaccine administration	0		
Record any concomitant medication/vaccination	●	●	●
Record any intercurrent medical conditions		●	●
Distribution of diary cards	0		
Recording of solicited adverse events (Days 0–3) by subjects	●		
Recording of non-serious adverse events (Days 0–30) post-vaccination, by investigator or subjects	●	●	●
Medically attended visits		●	●
Return of diary cards		0	0
Diary card transcription by investigator [‡]		●	●
Recording of serious adverse events (SAEs)	●	●	●
Recording of SAEs related to study participation or to a concurrent GSK medication/vaccine	●	●	●
Recording of pregnancies and pregnancy outcomes	●	●	●
Study Conclusion			●

PRE = Blood sample to be collected before vaccination, PD7 = Blood sample to be collected 7 days after vaccination, PD30 = Blood sample to be collected 30 days after vaccination

● is used to indicate a study procedure that requires documentation in the individual eCRF.

0 is used to indicate a study procedure that does not require documentation in the individual eCRF.

* Physical examination after the vaccination visit, will be performed only if the subject indicates during questioning that there might be some underlying pathology(ies) or if deemed necessary by the Investigator or delegate.

† Documentation regarding previous hepatitis B vaccination should be checked for subjects.

‡ Diary card will be returned to the subject to continue recording adverse events until the last Visit.

The intervals to be considered within the study are provided in [Table 6](#).

Table 6 Intervals between study visits

Interval	Optimal length of interval	Allowed interval ¹
Visit 1→ Visit 2	7 days	5 days - 12 days
Visit 1→ Visit 3	30 days	21 days - 48 days

¹ Subjects will not be eligible for inclusion in the ATP cohort for analysis of immunogenicity if they make the study visit outside this interval.

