5.6.17. Return of diary cards and diary card transcription by investigator

- Collect and verify completed diary cards during discussion with the subject at Visit 2 and Visit 3.
- Any unreturned diary cards will be sought from the subject through telephone call(s) or any other convenient procedure. The investigator or delegate will transcribe the collected information into the eCRF in English.

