- For the analysis of unsolicited adverse events/concomitant medication, all vaccinated subjects will be considered and subjects who did not report an event will be considered as subjects without an event.

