9.9. Analysis of safety

The primary analysis will be performed on the TVC.

- The percentage of subjects who reported at least one local AE (solicited and unsolicited), with at least one general AE (solicited and unsolicited) and with any AE during the 4-day (Days 0-3) follow-up period after the vaccination will be tabulated with exact 95% CI. The same calculations will be performed for any Grade 3 (solicited or unsolicited) symptoms and any symptoms requiring medical attention.
- The percentage of subjects reporting each individual solicited symptom during the 4-day (Days 0-3) follow-up period with exact 95% CI, by type of AE; by severity (any Grade, Grade 3 only); by relationship to vaccination (any relationship, related only) will be tabulated.
- The occurrence of fever will be tabulated per 0.5°C cumulative increments as well as the occurrence of Grade 3 fever (> 39.0 °C axillary temperature) with causal relationship to vaccination.
- The percentage of subjects reporting at least one report of unsolicited AE classified by the Medical Dictionary for Regulatory Activities (MedDRA) and reported within the 31-day (Days 0-30) follow-up period after vaccination will be tabulated with exact 95% CI. The same tabulation will be performed for Grade 3 unsolicited AEs and for unsolicited AEs with a causal relationship to vaccination.
- SAEs during the entire study period and withdrawals due to AEs and SAEs reported during the 31-day follow-up period after the challenge dose will be described in detail.

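### A compliant Visit 3 on Days 21-29 leaves up to 9 of the 31 days of unsolicited-AE follow-up without planned collection, so the reported percentage can be too low

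*Protocol*

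**What the plan says.** **Reporting window and denominator.** Protocol 9.9 (repeated in SAP 6.4.1) tabulates, on the total vaccinated cohort, the percentage of subjects with at least one unsolicited AE "reported within the 31-day (Days 0-30) follow-up period after vaccination". Protocol 9.5 keeps all vaccinated subjects in this analysis and adds that "subjects who did not report an event will be considered as subjects without an event". SAP 11.2.5 has the same rule, and SAP Template 26 takes as N the subjects with at least one administered dose.

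**Collection.** The footnote to Protocol Table 5 reads "Diary card will be returned to the subject to continue recording adverse events until the last Visit". Section 5.6.17 instructs sites as follows: "Collect and verify completed diary cards during discussion with the subject at Visit 2 and Visit 3". Study Conclusion is a Visit 3 procedure in Table 5, and under Section 8.1 a subject who attends that visit has completed the study.

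**Timing of Visit 3.** Table 6 gives 30 days as the optimal interval from Visit 1 and "21 days - 48 days" as the allowed one. Its footnote ties the interval to immunogenicity only: "Subjects will not be eligible for inclusion in the ATP cohort for analysis of immunogenicity if they make the study visit outside this interval".

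**Duty to record.** Section 5.6.15 has the subject note unsolicited AEs on the day of vaccination and the 30 days after it. Section 7.3.1 requires all AEs from Day 0 to Day 30 to be entered in the eCRF.

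**The concern.** The duty to record runs to Day 30, but the procedures that carry it out run to Visit 3, and the two ends need not coincide. A subject seen on Day 21 is fully compliant, hands in the diary, is concluded, and has no further scheduled contact. Nothing planned would pick up an event on Day 25, yet that subject enters the table as event-free for the whole 31 days.

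What is at stake is whether the 31-day label on a reported safety percentage is accurate. The error can go one way only, because missing days cannot add events. A Visit 3 after Day 30 does not compensate, since events after Day 30 fall outside the window. Template 26 makes no allowance for days actually observed. Solicited symptoms are handled differently: Protocol 9.5 and SAP 11.2.5 restrict that analysis to subjects with documented safety data.

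**Working it through.** **1. The plan's own figure.** Days 0 to 30 inclusive: 30 - 0 + 1 = 31 days. This agrees with the 31-day period in Protocol 9.9.

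**2. Days without planned collection.** Inputs: diary end at Visit 3 (Table 5 footnote) and Visit 3 allowed on Days 21 to 48 (Table 6). For Visit 3 on Day v, observed days = min(v, 30) + 1, and unobserved days = 31 minus that.

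| Visit 3 | Observed | Unobserved | Share of 31 |
|---|---|---|---|
| Day 21 | 22 | 9 (Days 22-30) | 29.0% |
| Day 25 | 26 | 5 | 16.1% |
| Day 30 | 31 | 0 | 0% |
| Day 48 | 31 | 0 | 0% |

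Nine days is the maximum inside the allowed interval. Because that interval governs only the immunogenicity cohort, a vaccinated subject seen before Day 21, or lost to follow-up, has more unobserved days and still counts as event-free if nothing was reported.

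**3. Effect on the percentage.** The documents give no AE rate and no distribution of visit dates, so everything in this step is assumed. With a constant daily hazard and a true 31-day risk p, the observable risk for Visit 3 on Day v is

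1 - (1 - p)^(d/31), where d = min(v, 30) + 1.

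*All subjects seen on Day 21, p = 30%:* 1 - 0.70^(22/31) = 22.4%.

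*Visits uniform over Days 21-48 (28 possible days), p = 30%:* 9 of the 28 days fall before Day 30 (9/28 = 32% of subjects). The mean loss is (9 + 8 + ... + 1)/28 = 45/28 = 1.6 days, or 5% of 31. The observable risks for Days 21 to 29 are 22.4, 23.3, 24.1, 25.0, 25.9, 26.7, 27.5, 28.4 and 29.2%, which sum to 232.4 before rounding. The other 19 days give 30% each. Study level: (232.4 + 19 × 30)/28 = 28.7%.

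*Range over assumptions:*

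| True 31-day risk | Uniform Days 21-48 | 25% on Day 21, rest Day 30 or later | All on Day 21 | All on Day 21, hazard halving every 7 days |
|---|---|---|---|---|
| 10% | 9.5% | 9.3% | 7.2% | 9.3% |
| 30% | 28.7% | 28.1% | 22.4% | 28.2% |
| 50% | 48.1% | 47.2% | 38.9% | 47.5% |

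The first three result columns use the constant hazard. If every subject is seen on Day 30 or later, the loss is zero in every row.

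**4. Scale.** The exact 95% CI for 30/100 is 21.2% to 40.0%, a half-width of (40.0 - 21.2)/2 = 9.4 points. The uniform scenario shifts the estimate by 30 - 28.7 = 1.3 points, about one seventh of that.

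**The case against.** **The diary is not the only instrument.** Table 5 has a row for non-serious AEs over Days 0-30 that names the investigator as well as the subject, and Section 7.3.3.1 requires active questioning. This is correct. But Table 5 marks that row at Visits 1 to 3 only, and the questioning is tied to visits too. Section 7.5.1.1 reviews ongoing AEs at later visits or contacts up to 30 days after vaccination, but none is scheduled after an early Visit 3.

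**The protocol already requires recording to Day 30.** Sections 5.6.15 and 7.3.1 say so, and Table 15 puts Visit 3, Day 30 and Study Conclusion in one column. An event on Days 22-30 is thus inside the reporting period and remains recordable if the investigator hears of it. That stands, and it makes this partly a matter of reconciling texts. It does not supply a contact: Section 7.3.2 does not oblige investigators to seek AEs in former participants. The telephone route of Section 5.6.17, "Any unreturned diary cards will be sought from the subject through telephone call(s) or any other convenient procedure", concerns diaries that were not handed in. The Study Procedures Manual might add instructions, but it is not part of the documents.

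**The effect is conditional and probably small.** This also stands. Day 30 is the optimal visit day, a uniform spread ignores that, and early clustering of events shrinks the loss. A reader might infer that the percentage will be understated, or that 30% would be reported as 22.4%. The documents support neither reading. They do not show that anyone attends before Day 30, and 22.4% needs every subject at the first allowed day.

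**Template 5 would reveal early visits.** In part: it gives the minimum and maximum vaccination-to-sample interval, so the earliest visit would show. It counts only intervals outside 21-48 days, not how many fall on Days 21-29.

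**Conclusion.** The point holds as a minor one. For any subject whose Visit 3 falls on Days 21-29, between 1 and 9 of the 31 days have no planned AE collection, while the subject stays in the denominator as event-free if nothing was reported. The percentage can therefore be biased downward, never upward, by this route. The day count follows from the documents alone.

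The size in percentage points does not. It rests on an assumed AE risk, hazard shape and spread of visits, and it runs from nothing (all subjects seen on Day 30 or later), through about 1.3 points at a true 30% with uniform visits, to 7.6 points (30 - 22.4) at the extreme. The endpoint is secondary, the study has a single arm, and all analyses are descriptive, so no comparison or decision rule depends on it.

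**What to change.** **If collection can still be changed:** reconcile the Table 5 footnote with Sections 5.6.15 and 7.3.1. Subjects whose Visit 3 falls before Day 30 would keep the diary to Day 30 and return it by the telephone or other route of Section 5.6.17, extended to cover them. The cost is one diary return or call for those subjects only.

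**If data are already collected:** state in Template 26 how many subjects were observed for less than Days 0-30, and repeat the percentage in subjects observed through Day 30. Visit dates are already recorded, so this costs one extra table.

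Either way, the allowed Visit 3 interval for immunogenicity stays as it is.

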9. STATISTICAL METHODS

9.1. Primary endpoint

- Persistence of immunity to hepatitis B in adult subjects vaccinated with three or four doses of *Engerix-B* 20 to 30 years ago.
 - Percentage of adult subjects with an anamnestic response 7 days and 30 days after the challenge dose.

Refer to Section 9.5 for the definition of anamnestic response.

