9.4.2. According-to-protocol cohort for analysis of immunogenicity

The ATP cohort for analysis of immunogenicity will include all evaluable subjects (i.e. those meeting all eligibility criteria, complying with the procedures defined in the protocol, with no elimination criteria during the study) who have received the challenge dose and for whom data concerning immunogenicity endpoint measures at pre-challenge (Visit 1) and one month post-challenge (V3) are available. The interval between Visit 1 and Visit 3, considered for inclusion of a subject in the ATP cohort for analysis of immunogenicity will be 21-48 days.

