9.5. Derived and transformed data

- Seronegative subjects:
 - Subjects with anti-HBs antibody concentration < 6.2 mIU/ml
- Seropositive subjects:
 - Subjects with anti-HBs antibody concentration ≥ 6.2 mIU/ml
- Seroprotected subjects:
 - Subjects with anti-HBs antibody concentration ≥ 10 mIU/ml

- Anamnestic response to the challenge dose is defined as:
 - At least (i.e. \geq) 4-fold rise in one month post-vaccination anti-HBs antibody concentrations in previously seropositive subjects.
 - In previously seronegative subjects, anti-HBs antibody concentrations ≥ 10 mIU/ml at one month post-challenge dose time-point.
- Amplitude of anamnestic response is the change in fold value from pre-challenge dose time-point to one month post-challenge dose.
- GMC calculations are performed by taking the anti-log of the mean of the \log_{10} concentration transformations. GMC will be calculated on all subjects. Antibody concentrations below the cut-off of the assay will be given an arbitrary value of half the cut-off for the purpose of GMC calculation.
- For a given subject and a given immunogenicity measurement, missing or non-evaluable measurements will not be replaced. Therefore, an analysis will exclude subjects with missing or non-evaluable measurements.

Safety/Reactogenicity:

For the analysis of solicited symptoms within 4 days (Days 0-3) post-challenge dose, missing or non-evaluable measurements will not be replaced. Therefore, the analysis of the solicited symptoms based on the TVC will include only subjects with documented safety data (i.e. symptom screen completed).

More specifically, the following rules will be used:

- Subjects who documented the absence of a solicited symptom after challenge dose will be considered not having that symptom after that dose.
- Subjects who documented the presence of a solicited symptom and fully or partially recorded daily measurement over the solicited period will be included in the summaries at the challenge dose and classified according to their maximum observed daily recording over the solicited period.
- Subjects who documented the presence of a solicited symptom after the challenge dose without having recorded any daily measurement will be assigned to the lowest intensity category at that dose (i.e. 37.5°C for fever or grade 1 for other symptoms).
- Doses without symptom sheets documented will be excluded.

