9.7. Analysis of immunogenicity

The primary analysis on the response to the challenge dose will be performed on the ATP cohort for analysis of immunogenicity. If the percentage of subjects excluded from the ATP cohort for immunogenicity is more than 5%, a second analysis based on the TVC will be performed to complement the ATP analysis of immunogenicity. The immunogenicity analysis based on the TVC will include subjects for whom immunogenicity data are available. All the immunogenicity analysis will be performed as a whole group and by age stratification. The age stratification will be 40-50 years and 51-60 years.

The following analyses will be performed:

- The percentage of subjects with anti-HBs antibody concentrations ≥ 6.2 mIU/ml, ≥ 10 mIU/ml, ≥ 100 mIU/ml, ≥ 1000 mIU/ml with exact 95% CIs will be calculated at the pre-challenge dose time-point, Day 7 and Day 30 post-challenge dose time-points.
- The percentage of subjects who mount an anamnestic response to the challenge dose, one month after vaccination, will be tabulated with exact 95% CI as a whole and according to their seroprotection status at pre-challenge time-point (anti-HBs antibody concentrations \leq or ≥ 10 mIU/ml).
- GMCs with 95% CI will be calculated for anti-HBs antibodies at the pre-challenge dose time-point, Day 7 and Day 30 post-challenge dose time-points.
- The distribution of anti-HBs antibody concentrations will be displayed using reverse cumulative distribution curve (RCC) at the pre-challenge dose time-point and Day 30 post-challenge dose time-point.
- Relationship between pre-challenge dose time-point and Day 30 post-challenge dose time-point results will be presented by regression line graph.
- CMI responses in terms of frequency of HBs-specific CD4 $^{+}$ T-lymphocytes and frequency of HBs-specific memory B cells at Day 0, Day 7 and Day 30 (for subjects who received a challenge dose) will be evaluated.
- The percentage of subjects with anti-HBs concentrations ≥ 6.2 mIU/ml, ≥ 10 mIU/ml and ≥ 100 mIU/ml (with 95% CI) at the Day 7 and Day 30 post-challenge dose time-points will be tabulated in relation to their pre-challenge dose status (overall, < 10 mIU/ml and ≥ 10 mIU/ml).
- The percentage of subjects (with 95% CI) who mount an anamnestic response will be calculated and in relation to their pre-challenge dose status (< 10 mIU/ml and ≥ 10 mIU/ml).

9.8. Exploratory Analysis:

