5. ANALYSIS SETS

5.1. Definition

Two cohorts are defined for the purpose of analysis

- Total Vaccinated Cohort(TVC) will include all subjects who received the challenge dose
- ATP cohort for analysis of immunogenicity (ATP Immunogenicity)- will include all evaluable subjects (i.e. those meeting all eligibility criteria, complying with the procedures defined in the protocol, with no elimination criteria during the study) who have received the challenge dose and for whom data concerning immunogenicity endpoint measures at pre-challenge (Visit 1) and one-month post-challenge (V3) are available. The interval between Visit 1 and Visit 3, considered for inclusion of a subject in the ATP cohort for analysis of immunogenicity will be 21-48 days

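### A mistimed Day 7 sample removes a subject's valid Day 30 response from the primary analysis, while no listed code removes a subject with no Day 7 sample

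*Protocol*

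**What the plan says.** **Visit windows.** Protocol 5.5, Table 6 allows 5-12 days from Visit 1 to Visit 2 and 21-48 days from Visit 1 to Visit 3. The shared footnote reads: "Subjects will not be eligible for inclusion in the ATP cohort for analysis of immunogenicity if they make the study visit outside this interval".

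**Elimination codes.** SAP 5.2.2.1 acts at subject level. Code 2090 covers a sample that was drawn off schedule or on an unknown date, and it lists both SER_2 (5-12 days) and SER_3 (21-48 days). Code 2100, for missing post-vaccination serology, lists only Visit 3 anti-HBs. SAP 5.2.2.3, on visit-specific censoring, is marked not applicable.

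**Cohort definition.** Protocol 9.4.2 asks for data at Visit 1 and Visit 3 and names one interval, 21-48 days: "The interval between Visit 1 and Visit 3, considered for inclusion of a subject in the ATP cohort for analysis of immunogenicity". SAP 5.1 does the same: "The interval between Visit 1 and Visit 3, considered for inclusion of a subject in the ATP cohort". The Day 7 window enters both only through a general clause on evaluable subjects: "complying with the procedures defined in the protocol, with no elimination criteria during the study".

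**Endpoint and analysis.** Protocol 9.5 and SAP 11.2.4 define the response as a "4-fold rise in one month post-vaccination anti-HBs antibody concentrations in previously seropositive subjects", or at least 10 mIU/ml at one month in those previously seronegative. Under Protocol 9.7, the percentage of subjects with "an anamnestic response to the challenge dose, one month after vaccination, will be tabulated". The primary endpoint in Protocol 9.1 and SAP 4 is worded more widely: "Percentage of adult subjects with an anamnestic response 7 days and 30 days after the challenge dose". The primary analysis uses the ATP cohort, with this supplement: "If the percentage of subjects excluded from the ATP cohort for immunogenicity is more than 5%, a second analysis based on the TVC" is added.

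**The concern.** The Day 7 window is reasonable for Day 7 results. The difficulty is its reach: a fault in one sample discards a different, valid sample that carries the tabulated primary response.

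The codes also work in an odd direction. A subject who attended Visit 2 late is removed, while one who gave no Visit 2 sample meets none of the listed codes. The subject who supplied more data is treated more harshly, and the cohort does not have common Day 7 and Day 30 membership either.

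At stake are avoidable losses from the primary analysis and an ATP definition that reads differently depending on whether one starts from Protocol 9.4.2 or from Table 6 and code 2090.

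**Working it through.** **1. Trace two subjects through the rules.** Both have valid anti-HBs at Visit 1 and a valid Visit 3 sample within 21-48 days.

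| | Subject A | Subject B |
|---|---|---|
| Visit 2 sample | Taken on day 13 | Not taken |
| Table 6 footnote | Outside 5-12 days: not eligible | No visit outside the window |
| Code 2090 | Applies (sample drawn, SER_2 off schedule) | Does not apply (needs a sample) |
| Code 2100 | Does not apply (Visit 3 present) | Does not apply (Visit 3 only) |
| Result under the listed codes | Out of ATP | In ATP |
| Anamnestic response computable as defined? | Yes | Yes |

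**2. Reproduce the planned precision.** Protocol 9.3 allows for 20% non-evaluable: 100 × (1 − 0.20) = 80. The interval is Clopper-Pearson (SAP 11.1): for x responders among n, the lower limit is the 2.5% quantile of Beta(x, n − x + 1) and the upper limit is the 97.5% quantile of Beta(x + 1, n − x). For 72/80 this gives 81.2-95.6, for 76/80 it gives 87.7-98.6, and for 80/80 it gives 95.5-100.0. All three match Table 18.

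**3. Vary the number excluded.** The documents give no rate of mistimed Day 7 samples, so the losses below are assumptions. Take about 100 vaccinated and about 95% response, with counts rounded to whole subjects. Widths come from unrounded limits.

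| Excluded in total | ATP N | Responders | 95% CI (%) | Width (points) |
|---|---|---|---|---|
| 100 − 95 = 5 | 95 | 90 | 88.1-98.3 | 10.1 |
| 100 − 94 = 6 | 94 | 89 | 88.0-98.3 | 10.2 |
| 20 (plan) | 80 | 76 | 87.7-98.6 | 10.9 |
| 100 − 78 = 22 | 78 | 74 | 87.4-98.6 | 11.2 |
| 100 − 72 = 28 | 72 | 68 | 86.4-98.5 | 12.1 |

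The last two rows represent 2 and 8 subjects lost beyond the 20% allowance.

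**4. Read this against the 5% trigger for the TVC analysis.**

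- *5% or fewer excluded.* N is at least 95, better than plan, and at most 5 subjects can be affected. The TVC analysis is not required, so a subject lost only for Day 7 timing need appear in no immunogenicity analysis.
- *More than 5% and up to 20%.* N is 80-94, at or above plan. The TVC analysis runs and includes these subjects.
- *More than 20%.* Precision falls slightly below plan. The TVC analysis runs, but ATP remains primary.

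Protocol 9.3 expects at least 20% non-evaluable, so a triggered TVC analysis is the planned case.

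**The case against.** The strongest defence is that this is a deliberate, pre-specified per-protocol rule. Table 6 and code 2090 agree on the window, the general compliance clause can carry it, and naming the Visit 3 interval in 9.4.2 does not say it is the only one. A single strict cohort also keeps the Day 7 and Day 30 tables on the same subjects. Day 7 is not incidental either: the primary endpoint wording names it, and Day 7 anti-HBs and cell-mediated responses are secondary endpoints. Finally, the 20% allowance already covers non-compliance, the study is descriptive with no test to flip, and the TVC analysis recovers the subjects in the expected scenario.

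The argument about size stands: the harm is small, and none of it depends on an established bias. The argument for common membership does not, because the listed codes leave in a subject with no Day 7 sample. The general clause could be stretched to exclude that subject too, but no code does so, which is itself a reason to align the texts. The wording of the primary endpoint does need settling, but either outcome leaves this point intact. If a Day 7 response is analysed, removing the mistimed Day 7 value protects that analysis. Protocol 9.5 and SAP 11.2.4 already leave out missing or non-evaluable values analysis by analysis.

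One caution is fair. SAP 5.3 says that the study team reviewed protocol deviations, without giving the timing. A change to cohort membership after that review should be documented as such.

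**Conclusion.** The concern holds. As written, a Day 7 sample outside 5-12 days removes the subject from the primary ATP cohort although the response as defined and tabulated does not use that sample, and no listed code removes a subject who has no Day 7 sample.

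The consequence is modest. With up to 20% excluded, precision is at or better than planned. If 2 to 8 of the 80 evaluable subjects were lost beyond the allowance, the lower limit would fall by 0.3 to 1.3 points and the interval would widen by 0.3 to 1.2 points. Part of that shift is count rounding, since 68/72 is 94.4% rather than 95.0%. These figures assume about 100 vaccinated, about 95% response and an assumed loss. No link between Day 7 timing and Day 30 response is assumed.

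The change should be made because it keeps valid primary data at almost no cost, not because the study's conclusions are at risk.

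**What to change.** - **Protocol Table 6 footnote:** state that only the Visit 1 to Visit 3 interval decides membership of the ATP immunogenicity cohort. This agrees with the interval already named in Protocol 9.4.2 and SAP 5.1.
- **SAP 5.2.2.1, code 2090:** delete the VAC_1 to SER_2 row and keep VAC_1 to SER_3 at 21-48 days. Limit the unknown-date condition to the vaccination date and the Visit 3 sample date.
- **SAP 5.2.2.3:** replace the not-applicable entry with: Visit 2 results (anti-HBs and cell-mediated) from samples taken outside 5-12 days after VAC_1, or on an unknown date, are excluded from Day 7 analyses only.
- **SAP Template 5:** keep reporting out-of-window Visit 2 samples.

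A subject with a late Day 7 sample and one with none are then handled alike: both stay in the cohort and neither contributes a Day 7 value.

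**Cost:** a protocol wording amendment and a short SAP edit, with no new data. N may differ slightly between Day 7 and Day 30 tables; Template 12 already defines N by available results. If deviations have already been reviewed, record the change and its timing in SAP section 9 and in the study report, as Protocol 9.11 requires for departures from the plan.
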